### 7.2.2.2 Intensity

The following 3-point rating scale must be used for rating of the intensity of each AE:

MILD:	THE EVENT IS EASILY TOLERABLE AND DOES NOT INTERFERE WITH NORMAL DAILY ACTIVITIES.
MODERATE:	THE EVENT IS TOLERABLE AND THE PATIENT IS ABLE TO PERFORM MOST OF THE DAILY ACTIVITIES.
SEVERE:	THE EVENT CAUSES INABILITY TO WORK OR PERFORM DAILY ACTIVITIES.

### 7.2.2.3 Causal Relationship to the IMP

The reporter must always report his/her evaluation of causal relationship between the event and the suspect drug. The causal relationship to the IMP must be rated using the following 2-point scale:

Term	Definition	Clarification
No reasonable possibility (not related)	This category applies to AEs which, after careful consideration, are clearly due to extraneous causes (disease, environment, etc.) or to AEs, which, after careful medical consideration at the time they are evaluated, are judged to be unrelated to the IMP.	An AE may be considered no reasonable possibility if it is clearly due to extraneous causes or when (at least 2 of the following): 
 
• it does not follow a reasonable temporal sequence from the administration of the IMP.
 
• it could readily have been produced by the patient's clinical state, environmental or toxic factors, or other modes of therapy administered to the patient.
 
• it does not follow a known pattern of response to the IMP.
 
• it does not reappear or worsen when the IMP is re-administered.
 

Reasonable possibility (related)	This category applies to AEs for which, after careful medical consideration at the time they are evaluated, a connection with the test drug administration can neither be ruled out with certainty nor felt with a high	An AE may be considered reasonable possibility related if or when (at least 2 of the following): 
 
• it follows a reasonable temporal sequence from administration of the IMP.
 
• it cannot be reasonably explained by the known characteristics of the patient's clinical state, environmental or toxic factors, or
 

	degree of certainty to be related to the IMP.	other modes of therapy administered to the patient. 
 
• it disappears or decreases on cessation or reduction in dose. There are important exceptions when an AE does not disappear upon discontinuation of the drug, yet drug-relatedness clearly exists.
 
• it follows a known pattern of response to the IMP.
 

--	---	---

#### 7.2.2.4 Action Taken to IMP

The action taken to the IMP in response to an AE must be classified as one of the following:

- None
- Discontinued
- Temporarily discontinued
- Dose decreased
- Dose increased

#### 7.2.2.5 Other Action Taken

AEs requiring therapy must be treated with recognized standards of medical care to protect the health and well-being of the patient. Appropriate resuscitation equipment and medicines must be available to ensure the best possible treatment of an emergency situation.

All actions taken to treat the event should also be reported. If medication is administered to treat the AE, this medication should be entered in the Concomitant Medication Log (regardless of seriousness).

#### 7.2.2.6 Date of Outcome/Time of Outcome

The date/time of outcome must always be collected when the event has recovered, recovered with sequelae, or the patient died. If an exact date is not available, the best possible estimate should be reported (e.g. in mid-January, 3 weeks ago, etc.).

#### 7.2.2.7 Outcome

The outcome of an AE must be classified as one of the following:

RECOVERED:	THE EVENT HAS FULLY RECOVERED. IF THE EVENT WAS WORSENING OF AN UNDERLYING MEDICAL CONDITION, THE EVENT IS CONSIDERED RECOVERED WHEN THE CONDITION HAS RETURNED TO THE INITIAL LEVEL.
RECOVERED WITH SEQUELAE:	THE EVENT HAS RECOVERED, BUT THE PATIENT HAS DEVELOPED CHRONIC SEQUELAE AS A CONSEQUENCE OF THE EVENT.
NOT YET RECOVERED:	THE EVENT WAS ONGOING AT THE TIME OF THE REPORT.
DEATH:	THE PATIENT DIED.

### 7.3 Follow-up of Adverse Events

During the study, the investigator (or qualified designee) must follow-up on each AE until it is resolved or until the medical condition of the patient is stable.

---

After the EOS, the investigator (or qualified designee) must follow-up on any AEs classified as serious or as related to the IMP until they are resolved, or until the medical condition of the patient is stable, or until 30 days (whichever comes first). All such relevant follow-up information must be reported to [REDACTED] Teva. If the event is a chronic condition the investigator (or qualified designee) and the Sponsor may agree if further follow-up is not required.

#### **7.4 Adverse Events of Special Interest**

##### **Seizure/Convulsion**

The investigator (or qualified designee) must **immediately** report any case of seizure(s) or convulsion(s) as a medically important SAE. The investigator (or qualified designee) shall report such cases to [REDACTED] Teva following the procedure and timelines for reporting of SAEs. Any patient that experiences a seizure must be withdrawn from the study.

##### **Pregnancy**

The investigator (or qualified designee) must **immediately** report all pregnancies in case any of the study patients or patient's partner becomes pregnant. If a study patient becomes pregnant, the IMP should immediately be stopped and the patient will be withdrawn. Note that pregnancy itself is not an SAE, however, pregnancy should be reported using the Pregnancy Report Form and should be reported within the same timelines as for SAEs.

All pregnancies which are identified during the clinical study must be followed up until delivery and 1 month after delivery or termination. Follow-up should be done using the Pregnancy Report Form.

In case a pregnancy results in an abnormal outcome an SAE Form must be filled in and reported within the timelines stated for SAEs.

##### **Suicidal Ideation or Suicidal Attempt**

AEs of suicidal ideation or attempt should be reported to the Sponsor within 24 hours of learning of the event (expedited reporting, regardless of seriousness). The corresponding dedicated eCRF should be completed, but the events should not be marked as serious unless deemed serious by the investigator (or qualified designee). The words "protocol defined AE" should be added after the AE term. Once the AE of suicidal ideation or attempt is received, the patient should be discontinued from the study and from IMP, and referred to a psychiatrist for evaluation and monitoring (see Section [7.7.2](#)).

Standard emergency medical procedures should be followed for any medical and safety concern when immediate intervention is needed (refer to protocol-specific Escalation Plan).

##### **Reportable Events**

If a patient stops IMP due to intolerability or an adverse reaction, the site must notify the [REDACTED] within 72 hours after being informed that treatment was stopped.

Patients who discontinue treatment with IMP due to safety or tolerability reasons may continue in the study off IMP and perform the scheduled visits and assessments.

---

## **7.5 Serious Adverse Events**

### **7.5.1 Definitions**

#### **7.5.1.1 Serious Adverse Event (SAE)**

A SAE is any untoward medical occurrence that at any dose:

- Results in death,
- Is life-threatening,
- Requires inpatient hospitalization or prolongation of existing hospitalization
- Results in persistent or significant disability/incapacity
- Is a congenital anomaly/birth defect,
- Other important medically condition.

An AE caused by an overdose or medication error is considered serious if a criterion listed in the definition above is fulfilled.

### **7.5.2 Collection and Recording of Serious Adverse Events**

#### **7.5.2.1 Serious Adverse Event Form (SAE Form)**

The investigator (or qualified designee) must capture information for each SAE on the SAE Form. The information captured should be the same as described in above sections for AEs. In addition the following information must also be provided:

- Medical history
- Other relevant clinical findings
- Narrative
- Reason for seriousness
- Concomitant medications

All the information provided in the SAE Form **must** match the information captured in the eCRF.

#### **7.5.2.2 Medical History**

Relevant updated medical history should be reported with as detailed information as possible including medical term, onset date, and stop date (if not ongoing).

#### **7.5.2.3 Other Relevant Clinical Findings**

Other information relevant to the SAE such as hospital records, results from investigations e.g. laboratory parameters, invasive procedures, scans and x-rays, and autopsy results should be summarized in the narrative, can be attached to the SAE Form, and must, in any

---

 Life-threatening refers to an event in which the patient was at risk of death at the time of the event; it does not refer to an event which hypothetically might have caused death if it were more severe.

 Inpatient hospitalization or prolongation should be interpreted as admission for 24 hours or more. Pre-planned hospital admission prior to the start of the study is not considered hospitalization.

 Medical judgment should be exercised in deciding whether an AE is serious in other situations. Important AEs that are not immediately life-threatening or result in death or hospitalization but may jeopardize the patient or may require intervention to prevent one of the outcomes listed in the definition above should also be considered serious.

 Patient details such as name, address, hospital ID number, etc. must always be concealed before sending copies to Teva.

case, be supplied from the investigator (or qualified designee) upon request from the Sponsor. The documents should be provided in English or translated into English.

#### 7.5.2.4 Narrative

The investigator (or qualified designee) must write a narrative of the clinical course leading up to and following the event and provide this narrative in the SAE Form sent to Teva. The narrative should summarise all relevant clinical and related information, including patient characteristics, therapy details, prior medical history, clinical course of the event, and laboratory values. The narrative should be presented in a logical time sequence and give a full overview of the cause of event(s), making the case understandable to persons without existing knowledge of the patient and without access to the patient's hospital records. If laboratory results are presented, reference ranges should be included. If the patient was hospitalized, dates of hospital admission and discharge should be included.

#### 7.5.3 SAE Reporting Responsibilities of the Investigator (or Qualified Designee)

All SAEs must **immediately** be notified to the [REDACTED] Teva as soon as it becomes known to the investigator (or qualified designee) and not later than within 24 hours of their knowledge of the occurrence of an SAE according to contact details given below. The notification shall at minimum contain investigational site ID, patient ID, AE, investigator causality, and seriousness criterion.

The investigator (or qualified designee) must transmit the completed SAE Form with the fullest possible details to **Teva Pharmaceuticals** by fax or e-mail **within 2 calendar days** of their knowledge of the SAE.

Serious Adverse Event Reporting Contact Information
[REDACTED]

It is the responsibility of the investigator (or qualified designee) to comply with their local institutional review board (IRB) or research ethics board (REB) regulations regarding the reporting of AEs.

Standard emergency medical procedures should be followed for any medical and safety concern when immediate intervention is needed (refer to protocol-specific Escalation Plan).

#### 7.5.3.1 SAEs Occurring After End-of-Study

If the investigator (or qualified designee) becomes aware of an SAE after the EOS, which he/she assesses to be related to the IMP, the SAE should be reported to Teva. This applies no matter how long after the end of the study the SAE occurred.

#### 7.5.4 Emergency Contact

In case of emergency or and/or where further advice is required regarding the handling of SAEs, the emergency 24 hour contact phone number should be used.

EMERGENCY CONTACT: [REDACTED]
--------------------------------------

Emergency calls will be handled by a fully qualified clinician. A clinician will be available 24 hours a day, 7 days a week on the telephone number above.

## **7.6 Expedited Reporting by Teva**

### **7.6.1 Responsibilities**

Teva is responsible for reporting relevant safety information to all regulatory authorities, investigators (or qualified designees), and central IRBs/ethics committees (ECs).

### **7.6.2 Expedited Reporting**

All AEs that are **serious, unexpected, and considered related to the IMP** judged by either the investigator (or qualified designee) or Teva require expedited reporting.

The expectedness is assessed by Teva according to the (Investigator's Brochure) IB in force at the time of the event.

All available information relevant to the evaluation of the SAE will be reported.

SAEs will be considered reportable regardless of whether or not the IMP was used in accordance with the provisions in the Protocol and/or the IB.

#### **7.6.2.1 Timelines for Expedited Reporting**

**Fatal or life-threatening serious, unexpected, related** cases occurring in clinical studies require very rapid reporting. Regulatory authorities, ECs and investigators (or qualified designees) shall be notified (e.g. by telephone, facsimile transmission, or in writing) as soon as possible but **no later than 7 calendar days** after first knowledge by Teva. This should be followed by a report that must be as complete as possible within 8 additional calendar days.

**Serious cases that are unexpected and related and are not fatal or life-threatening**, must be submitted as soon as possible but **no later than 15 calendar days** after first knowledge by Teva that the case meets the minimum criteria for expedited reporting.

## **7.7 Premature Discontinuation of Treatment**

If a patient prematurely discontinues treatment the reason for discontinuation should be recorded on the eCRF.

In the event of tolerability problems during the first 4 weeks, patients will be instructed to immediately contact their investigator (or qualified designee) to discuss their AE(s). Patients who experience any intolerable AEs during the first 4 weeks of the study that, in the opinion of the investigator (or qualified designee) could be related to IMP, will attend an EOT visit and discontinue IMP. In the event of tolerability problems during the remainder of the study, please refer to Section [5.3.1](#).

### **7.7.1 Cessation of Treatment**

A patient will be classified as having ceased treatment when he or she discontinues IMP, prior to the completion of the prescribed course for any of the following reasons:

- AE
- Death
- Lost to follow up
- Patient withdrew consent
- Major protocol violation
- Pregnancy

- 
- Treatment is no longer appropriate
  - Termination of study

If hypokalemia is observed, dosing will be interrupted and should not be started again until normal electrolyte values are confirmed by re-draw and maintained for 7 days. Patients needing more than 14 days to reach stable potassium levels, without IMP, should be withdrawn from the IMP. The patient will be asked to continue in the study and follow the visit schedule as outlined in the protocol.

In instances where there is an increase in QT/QTcF of >500ms or 60ms over VTV, a second ECG should be repeated after 10 minutes rest to confirm the finding. Where confirmed, this should be reported and documented on the eCRF as an AE.

Patients with a QTcF interval of >500 ms, or with an increase in the average QTcF value >60 ms from the VTV, should be discontinued from the study. A follow-up ECG should be done in 4 weeks.

Patients should also be discontinued if:

- they experience a seizure or convulsions (regardless of the relationship to treatment);
- their body weight decreases to <50 kg (may be discontinued based on investigator (or qualified designee) or Sponsor discretion);
- and/or if creatinine clearance decreases to <60 mL/min (calculated using the Cockcroft-Gault equation). It is allowed to repeat the test once, if clinically appropriate.
- they experience an AE/SAE of suicide ideation or attempt; or
- they have a C-SSRS suicidal ideation score  $\geq 3$  (i.e. who answer "Yes" to questions 3, 4, and 5 in the scale suicidal ideation section); or
- they have a C-SSRS report of suicidal act; or
- they have an abbreviated PBA-s suicidal ideation item score  $\geq 3$  (i.e. 3, 4).

Patients who discontinue treatment with IMP due to safety or tolerability reasons may continue in the study off IMP and perform the scheduled visits and assessments.

### **7.7.2 Withdrawal**

Patients have the right to discontinue IMP at any time and for any reason. The investigator (or qualified designee) also has the right to discontinue IMP if he/she feels that treatment is no longer appropriate, if in his/her opinion the patient's clinical condition is worsening or for an AE(s).

A complete evaluation, as detailed in the study protocol for the EOS Visit, should be carried out at the time of discontinuation. The patient will then be withdrawn from the study.

If the reason for premature discontinuation is an AE or an abnormal laboratory test result, the principal specific event or test must be reported on the appropriate section(s) of the eCRF.

All patients for whom an AE of suicidal behavior/ideation was reported at any time during the study should be discontinued from IMP and the need for an evaluation by a psychiatrist should be assessed. Discontinued patients should attend an ET visit remotely to return IMP, perform IMP accountability, and will be asked to complete all protocol required study procedures. AEs of suicidal behavior/ideation should be followed until resolution of the suicidal behavior/ideation.

All patients who are discontinued from the IMP due to active suicidal behavior/ideation should be referred to a psychiatrist and followed by the investigator (or qualified designee) until resolution of the suicidal behavior/ideation.

Patients who discontinue IMP due to safety or tolerability reasons may continue in the study off drug and perform the scheduled visits and assessments.

A patient will be considered to have withdrawn from a study in the following circumstances: death, lost to follow-up, if the patient has withdrawn informed consent, or the investigator (or qualified designee) feels that the treatment is no longer appropriate. If withdrawal is due to an SAE the procedure detailed in Section 7.5.3 should be followed.

Patients with a QTcF interval of >500 ms or if an increase in the average QTcF value is >60 ms from the VTV should be discontinued from the study. A follow-up ECG should be done in 4 weeks.

### **7.8 Replacement Policy for Patients Who Withdraw**

There will be no replacement of patients that withdraw from the study. Patients withdrawing will not be replaced.

### **7.9 Safety Monitoring**

The Sponsor is responsible for continuous safety monitoring, including all AEs, monitoring reports, and any other safety-related information.

During the conduct of this study, an Internal Safety Committee reviews accumulating safety data on a quarterly basis (or meet ad-hoc if a safety concern arises, as detailed in the Internal Safety Committee charter), to ensure the continuing safety of the study patients and study conduct issues.

The Internal Safety Committee receives safety data periodically in an unblinded fashion. They have the right to recommend discontinuation of the study for safety reasons.

All Internal Safety Committee sessions are open. The conduct and specific details regarding the Internal Safety Committee sessions are outlined in the Internal Safety Committee charter.

## **8 STATISTICAL ANALYSIS**

### **8.1 General Statistical Issues**

Continuous data will be summarized using descriptive statistics where the following will be reported:

- n (number of observations)
- Number of missing observations
- Mean
- Standard deviation
- Minimum
- Median
- Maximum

Categorical data will generally be presented using count and percentage. Specifications will be detailed in the statistical analysis plan.

## **8.2 Data Sets**

The analysis set for safety analysis is defined as all patients who were enrolled in the HART or PRIDE-HD studies and who received IMP, or who continued treatment in the Open-HART study.

The analysis set for efficacy analysis is defined as all patients who were enrolled in the HART or PRIDE-HD studies or continued treatment in the Open-HART study and for whom there is at least one post-virtualization visit with efficacy data.

## **8.3 Missing Values**

Missing values will not be imputed.

## **8.4 Sample Size and Power Considerations**

As this is an open-label extension study, no sample size calculations have been performed.

## **8.5 Disposition of Patients**

The number of patients who entered the study, who completed, and who discontinued prematurely will be tabulated.

Discontinuation will also be summarized by appropriate intervals (every 6 months).

## **8.6 Demographics and Other Baseline Characteristics**

Demographics and baseline characteristics will be tabulated.

## **8.7 Concomitant Medication During the Study**

Concomitant medication during the study will be listed.

## **8.8 Efficacy Set**

Descriptive statistics of each of the efficacy variables for the efficacy analysis set will be presented by yearly intervals. Changes in efficacy parameters will be calculated both from baseline (in main study) and from start of this extension part.

The efficacy parameters will also be presented graphically.

Efficacy data will be presented for all patients combined.

## **8.9 Assessments and Analysis of Safety and Tolerability**

### **8.9.1 Exposure**

The overall exposure in terms of patient-years will be presented by treatment. The number of patients who had a dosage reduction and who had a suspension of IMP will be presented.

### **8.9.2 Adverse Events**

All AEs starting either after the first dose and until 2 weeks after the last dose (scheduled follow-up period) in Open-HART, or Open-PRIDE-HD and continuing in the virtualized Open-HART or starting after the first dose in the Open-HART virtualization will be reported and regarded as treatment-emergent.

Separate displays will be presented for events starting in the Open-HART virtualization. In these displays, only an overall pridopidine treatment group will be presented. Both crude incidences and incidence rates (patients with events per exposure) will be presented.

Combined AEs from HART and Open-HART (ACR16C009 and ACR16C015, respectively) will be reported through an Integrated Summary of Safety.

The following displays will be generated:

- A brief summary of AEs will be tabulated.
- AEs will be summarized by system organ class and preferred term, severity, and relationship to IMP.
- Separate displays of SAEs and AEs leading to discontinuation will be produced.
- All AEs will be listed.

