#### 4.6 Conduct of the Study

The ACR16C015 (Open-HART) open-label extension study began in 2011 and has been ongoing in the United States and Canada (see [Appendix 1](#)) to evaluate the long-term safety and tolerability of pridopidine administered at a dose of 45 mg bid in adult patients with HD

who completed the treatment period of the HART or PRIDE-HD studies. The primary reason for this amendment is to evaluate the feasibility of virtual study conduct and remote assessments administered in adult patients with HD receiving pridopidine 45 mg bid. All clinical sites will conduct study assessments remotely. The study will consist of a VTV, an open-label treatment period, and a follow-up period (30 days after end of treatment). The study will continue under the same study number; however, all patients will have to be re-consented regardless of their current study status. A CRO will provide oversight and many functions will be performed centrally. The study will include both remote visits and safety telephone contacts (TC). Remote visits will be considered "virtual" visits and will be conducted by investigators (or qualified designees) via real-time video conferencing. Other procedures will be performed by qualified nurses who will visit the patients' homes (and/or applicable locations).

If patients have concerns about the virtual nature of the site visits, they may request an unscheduled visit (USV) at the investigational center. The medical monitor will review individual requests and may approve 1 site USV per patient, per year. The assessments at site USVs will mirror those obtained during safety evaluation TCs (see Section 4.6.4). The investigator (or qualified designee) may schedule additional site visits on a case-by-case basis for patients that require closer monitoring due to safety events.

Patients excluded from the study due to lack of internet connection or inability to transition from in-person study visits to virtual study visits may be eligible to enroll in the Open-PRIDE-HD study (Study TV7820-CNS-20016).

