#### **4.6.9 Withdrawal From Treatment**

If the patient wishes to stop treatment, is judged by the investigator (or qualified designee) to not be suitable for continued therapy, or the study is discontinued, a remote visit ("withdrawal visit", ET visit) should be performed and the patient withdrawn from the study. A (telephone) follow-up visit (30 d TC follow up) to collect and report AEs, concomitant medications (as well as inquiry about changes in use of benzodiazepines and antidepressants), changes in use of alcohol and drugs associated with substance abuse (legal or illicit), C-SSRS, and an abbreviated PBA-s assessment should take place 1 month after the actual discontinuation of IMP took place.

Additional criteria for discontinuation of IMP for individual patients are detailed in Section [7.7.1](#).

Patients who discontinue IMP due to safety or tolerability reasons may continue in the study off IMP and perform the scheduled visits and assessments.

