##### **7.1.3 Treatment-Emergent Adverse Event**

A treatment-emergent AE is any AE occurring after start of IMP and within the time of residual drug effect, or a pre-treatment AE or pre-existing medical condition that worsens in intensity after start of IMP and within the time of residual drug effect.

The time of residual drug effect is the estimated period of time after the last dose of the IMP, where the effect of the product is still considered to be present based on PK, pharmacodynamics, or other IMP characteristics. The time of residual drug effect is for most drugs 5 half-lives of the IMP.

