#### **Withdrawal from treatment**

If the patient wishes to stop the drug, or is judged by the investigator to not be suitable for continued therapy, or the study is discontinued, a clinic visit ("withdrawal visit", end of study drug visit) should be performed and the patient withdrawn from the study. A (telephone) follow-up visit (30 d TC F/U) to collect and report AEs (as well as inquiry about changes in use of benzodiazepines and antidepressants, and inquiry about changes in use of alcohol and illicit drugs), C-SSRS and an abbreviated PBA-s assessment should take place one month after the actual discontinuation of study drug took place.

Patients who discontinue study medication due to safety or tolerability reasons may continue in the study off drug and perform the scheduled visits and assessments.

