### **7.3. Adverse Events**

All AEs will be coded using the MedDRA. AEs occurring on or after the first day of study drug administration will be included in the summaries. Summaries will be presented for all AEs (overall and by severity), AEs determined by the investigator to be related to study drug (overall and by severity), serious AEs, AEs leading to withdrawal from the study, and non-serious AEs.

The incidence and total number of AEs will be summarized using descriptive statistics by SOC and PT (all AEs overall will also be presented by just PT category). For the incidence of AEs, patients are counted only once in each SOC category, and only once in each PT category. The exposure adjusted incidence rate will also be presented and is defined as the number of patients with an AE divided by patient-years of treatment. For calculating patient-years, patients with an AE contribute with treatment exposure up to the day of their first AE, and patients without an AE contribute with the entire treatment exposure. For the summary by severity, patients are counted at the greatest severity. AEs missing relationship to study drug will be included in the study drug related summary.

In addition, a summary of AEs by time period of treatment will be presented.

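### The one-month safety call has a ±30-day window that reaches back to the last dose, and Protocol 8.9.2 labels two weeks as the follow-up period

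*Protocol*

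**What the plan says.** **Length of follow-up.** Protocol 4.6 describes "a follow-up period (30 days after end of treatment". Protocol 4.6.9 provides for "A (telephone) follow-up visit (30 d TC follow up) to collect and report AEs" and says that it "should take place 1 month after the actual discontinuation of IMP took place"; the synopsis has the same arrangement. The SAP, written on Amendment 04, says in its section on withdrawal from treatment that the call "should take place one month after the actual discontinuation of study drug took place".

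**Window for the call.** In the post-virtualization schedule (Protocol 1.3), the follow-up column is a telephone contact with the week number left as a placeholder and a window of ±30 days. It carries AE review, C-SSRS and the abbreviated PBA-s.

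**Cut-off for treatment-emergent events.** Protocol 8.9.2 has two limbs. The first takes events starting after the first dose and "until 2 weeks after the last dose (scheduled follow-up period) in Open-HART" or Open-PRIDE-HD that continue into the virtual phase. The second takes events starting after the first dose in the virtual phase and gives no end date. Protocol 7.1.3 uses a different rule, residual drug effect, without a number of days: "The time of residual drug effect is for most drugs 5 half-lives of the IMP". SAP 7.3 says "AEs occurring on or after the first day of study drug administration will be included in the summaries" and sets no end. SAP Section 9 reports no changes from the protocol's analyses.

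**The concern.** Two things do not fit together.

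First, the window for the safety call is as wide as the interval it is meant to measure. The call exists to learn what happens after the drug is stopped. If it can be made on the day of the last dose and still comply, that purpose is not secured. This matters most for patients who leave when they stop treatment, because no later contact is scheduled for them. The content is not trivial in this population: Protocol 2.1 reports that patients with HD commit suicide 4 to 8 times more often than the general population.

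Second, Protocol 8.9.2 does not merely choose a two-week analysis window. It labels those two weeks as the scheduled follow-up, which contradicts the one-month follow-up in Protocol 4.6, Protocol 4.6.9 and the SAP. Long-term safety is part of the primary objective, so the period over which events count as treatment-emergent should be stated once and in the same way in both documents.

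**Working it through.** There is no sample-size or power figure to reproduce. The check is day arithmetic and a comparison of the texts.

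**Inputs**
- Target for the call: 30 days or one month after IMP stops (Protocol 4.6 and 4.6.9; SAP, withdrawal from treatment).
- Window for the call: ±30 days (Protocol 1.3, follow-up column).
- Limit in the first limb of Protocol 8.9.2: 14 days after the last dose.
- Window for the numbered visits from Week 13 on: ±14 days (Protocol 1.3 and Section 6).

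**Step 1: permitted dates for the call.** Earliest = target − 30; latest = target + 30.

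| Target (days after last dose) | Earliest | Latest |
|---|---|---|
| 28 (short month) | −2 | 58 |
| 30 | 0 | 60 |
| 31 (long month) | 1 | 61 |
| 14 (if two weeks were the target) | −16 | 44 |

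With the 30-day target, 61 calendar days are permitted (day 0 to day 60), and 14 of them (day 0 to day 13) come before even the two-week mark. None of these targets keeps a ±30-day window more than one day clear of the last dose.

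**Step 2: comparison with other visits.** The first numbered contact with a ±14-day window is at Week 13, so its earliest date is 13 × 7 − 14 = 77 days after the Virtual Transition Visit. The other windows do not reach their anchor; this one does.

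**Step 3: can the two-week label be derived from any scheduled follow-up?** No. Every scheduled follow-up after the last dose in either document is at 30 days or one month. Two weeks appears as a follow-up length only in Protocol 8.9.2.

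**Step 4: which events does the two-week limit touch?** Protocol 4.6 describes the 30-day follow-up of the virtual phase, and an event starting on, say, day 20 after the last dose in that phase falls under the second limb, which has no end date. The gap 30 − 14 = 16 days is therefore a difference between two stated lengths. It does not measure events lost.

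**Step 5: protocol against SAP.** The first limb of 8.9.2 ends at 14 days; SAP 7.3 has no end. The rules differ in form, and SAP Section 9 does not say so.

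**Step 6: alternative windows** (illustrative, not in the documents). 30 ± 7 gives day 23 to day 37. 30 with +14 only gives day 30 to day 44. Neither reaches the last dose, and only the second guarantees a full 30 days of observation.

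**The case against.** The strongest reply has four parts.

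*Day 0 is constructed.* The schedule cell has no target week, and neighbouring cells hold unfilled placeholders, so ±30 days may be a slip for a 30-day target. A day-0 call would also go against Protocol 4.6.9. This is fair as to intent. But applying a schedule window to the target in the text is the normal reading, and a site following the table would comply with it. The cell needs correcting under either explanation.

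*Events are not lost.* A reader might infer that 16 of the 30 follow-up days (53%) go unreported, or that the call collects events that the analysis then discards. The documents do not support this. The limit applies to the carry-over limb only, Protocol 8.9.2 lists all AEs, and SAP 7.3 has no upper cut-off. The SAP's introduction says that it prevails where the two differ. This part of the objection stands.

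*The amendment was not implemented.* SAP 2.1 says so of Amendment 05, which introduced virtualization, so the window in Protocol 1.3 may have governed no visit. This also stands. The pre-virtualization schedule (Protocol 1.2) has no readable content in the public text, so the window then in force is unknown. The Amendment 04 wording of 8.9.2 is not available either, so the undeclared difference is shown only against the published protocol.

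*Other safeguards exist.* A reader might infer that suicidality after stopping goes unmonitored. That is too strong. The exit visit includes the C-SSRS, patients who stop for safety or tolerability may stay on with scheduled contacts, and suicidal events are followed to resolution (Protocol 7.7.2). Serious or related AEs are followed for up to 30 days after study end (7.3), and related SAEs remain reportable at any time (7.5.3.1). These provisions act at exit, on patients who stay, or on events already known. None schedules detection of new symptoms in a patient who has left.

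**Conclusion.** The point holds as a minor inconsistency in two parts.

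- The call window, combined with the 30-day target, permits day 0 to day 60, so the one scheduled contact after a patient leaves may observe no off-drug time. With one month read as 28 to 31 days, the earliest permitted date ranges from day −2 to day 1, so the conclusion does not depend on that reading. It does assume that the window in Protocol 1.3 applies to the target in 4.6 and 4.6.9.
- The two-week label in Protocol 8.9.2 contradicts the one-month follow-up. Its limit also differs from SAP 7.3, and SAP Section 9 does not declare this.

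No loss of events in the reported analysis is shown, and the 53% should not be cited as one. The practical effect on collected data is also limited if, as the SAP states, Amendment 05 was not implemented.

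**What to change.** 1. In Protocol 1.3, state the follow-up call as 30 days after the last dose with a window that cannot reach that dose, for example +14 days or ±7 days. The one-sided window is preferable because it always covers the full 30 days.
2. In Protocol 8.9.2, replace the two weeks with the 30-day follow-up. If two weeks is meant as an analysis limit, keep it but remove the label that calls it the scheduled follow-up.
3. In SAP 7.3, state the same AE cut-off. If the SAP is meant to have no upper limit, declare that difference in SAP Section 9.

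The cost is one table cell and a few lines of wording, with no new visit or data. The only operational burden is a somewhat tighter scheduling window for one telephone call.
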